10 INVESTIGATIONAL MEDICINAL PRODUCT DISCONTINUATION AND WITHDRAWAL

In accordance with the Declaration of Helsinki, the International Council for Harmonisation (ICH) Harmonised Guideline: Integrated Addendum to ICH E6(R1): Guideline for Good Clinical Practice (GCP) E6(R2), the FDA regulations relating to GCP and clinical trials, the EU Clinical Trials Directive, the EU GCP Directive and/or other applicable regulations, a participant has the right to withdraw from the trial at any time and for any reason, with no obligation to provide a reason, and without prejudice to his or her future medical care by the physician or at the institution.

The participant must be permanently discontinued from IMP if any of the following apply:

- Administrative decision by the investigator, GW, or a regulatory authority.
- Withdrawal of participant consent.
- Lost to follow-up.
- Pregnancy.
- QTcF \geq 500 msec (average of 3 measurements).
- Suicidal ideation or behavior of type 4 or 5 during the treatment period, as evaluated with the adult C-SSRS or based on investigator assessment.
- Protocol deviation that is considered to potentially compromise the safety of the participant or validity of data collected.
- ALT or AST > 3 × ULN with the appearance of fatigue, nausea, vomiting, right upper quadrant pain or tenderness, fever, rash, and/or eosinophilia (> 5%).
- ALT or AST $> 8 \times ULN$.
- ALT or AST $> 5 \times$ ULN for more than 2 weeks.
- ALT or AST $> 3 \times$ ULN and (TBL $> 2 \times$ ULN or INR > 1.5).

Note: Prior to treatment discontinuation for the transaminase elevations noted above, the investigator may choose to confirm the transaminase elevations by repeating the following laboratory tests within 24 to 48 hours: ALT, AST, TBL, INR, % eosinophils, gamma-glutamyl transferase (GGT), and alkaline phosphatase. Should the above transaminase elevation criteria be confirmed, the participant must permanently discontinue IMP. In cases where

Study Code: GWAP19030

EudraCT Number: 2019-003369-16 Clinical Protocol Global V3, 23Mar2021

transaminase elevation IMP discontinuation criteria are not met or confirmed, the dose of a concomitant medication with known hepatotoxicity may be reduced.

Should a participant request or decide to withdraw from the trial, all efforts must be made to complete and report the observations as thoroughly as possible up to the date of withdrawal. Participants withdrawing due to an AE should be followed up according to Section 12.7. All information should be reported on the applicable eCRF pages. A safety follow-up visit should take place 2 weeks after last dose of IMP. If withdrawing participants decline to give a reason for withdrawal of consent, the investigator must respect the participant's wishes.

EudraCT Number: 2019-003369-16 Clinical Protocol Global V3, 23Mar2021

11 URGENT SAFETY MEASURES

The sponsor and investigator may take appropriate urgent safety measures in order to protect the participants of a clinical trial against any immediate hazard to their health or safety. If such measures are taken by the investigator, they must notify GW immediately or at least within 24 hours of awareness. GW will report urgent safety measures to regulatory authorities by telephone within 24 hours of awareness, wherever possible, and will provide a written report to the regulatory authorities and IRB/IEC within 3 days.

Confidential Page 68 of 104
Clinical Protocol Template (Phase 2–4)

EudraCT Number: 2019-003369-16 Clinical Protocol Global V3, 23Mar2021

12 ADVERSE EVENT REPORTING

12.1 Definitions

12.1.1 Adverse Event

For the purposes of this trial an AE is defined as:

Any new unfavorable/unintended signs/symptoms (including abnormal laboratory findings when relevant), or diagnosis or worsening of a pre-existing condition, which occurs following screening (Visit 1) and at any point up to the post-treatment, safety follow-up visit (Visit 8), which may or may not be considered to be related to the IMP. Any event that is the result of a trial procedure must be recorded as an AE.

Surgical/investigational procedures are not AEs. The medical reason for the procedure is the AE. Elective hospitalizations for pre-trial existing conditions or elective procedures are not AEs. The exception may be if the participant has an AE during hospitalization that prolongs their scheduled hospital stay in which case it would be considered a SAE (refer Section 12.2).

If reporting a fatal event, the SAE term should be the underlying cause of the death (e.g., disease or medical condition leading to death).

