4 EXPERIMENTAL PLAN

4.1 Trial Design

This is a randomized, double-blind, placebo-controlled, parallel-group, outpatient trial. The trial will compare the efficacy and safety of 2 dose levels of GWP42003-P (150 mg twice daily [b.i.d.] and 500 mg b.i.d.) versus placebo in participants with schizophrenia who are experiencing an inadequate response to ongoing antipsychotic treatment.

The duration of the trial will be approximately 20 weeks, which includes a screening period (up to 4 weeks), a single-blind placebo run-in period (2 weeks), a double-blind treatment period (12 weeks), and a safety follow-up period (2 weeks).

After signing the informed consent form (ICF), participants will enter the screening period (Visit 1). The investigator will submit participants' eligibility forms for clinical surveillance and training (CST) review. The CST will evaluate the eligibility of participants and provide the outcome of the evaluation to the site. Participants cannot be enrolled until site personnel have received the final CST notification. Additional details for CST will be described in the study manual. At Visit 2 screened participants who continue to meet eligibility criteria will be randomized 1:1 to receive 150 mg b.i.d. or 500 mg b.i.d. dose matched volumes of placebo in a single-blind manner for the placebo run-in period. At Visit 3 (Day 1), participants who continue to meet the required eligibility criteria will be randomized 2:1 to receive GWP42003-P or placebo of equivalent volume to their placebo run-in allocation (Table 7.1-1) in a double-blind manner for the treatment period.

Randomization will be stratified by region (North America, Europe) and by sex (male, female).

A safety follow-up visit will be conducted 2 weeks after the last dose of IMP. If a participant discontinues IMP prematurely (i.e., before the end of the treatment period) they are required to attend an end of treatment (EOT) visit (±3 days) and complete the safety follow-up visit 2 weeks after their last dose. Participants are encouraged to attend any outstanding visits per the trial schema. If a participant prematurely discontinues IMP and withdraws from the trial without continuing trial visits as per the trial schema, they are required to attend an early termination (ET) visit upon withdrawal and complete the safety follow-up visit 2 weeks after their last dose.

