9.1.16 Adverse Events

All AEs will be recorded on the eCRF. All AEs occurring during the trial, whether attributed to the IMP or not, observed by the investigator or reported by the participant will be recorded in the eCRF, questioning the participant further if necessary.

Serious adverse events (SAEs) must be reported to GW Pharmacovigilance Department (PVD) within 24 hours of discovery or notification of the event via recording in the eCRF.

Refer to Section 12 for definitions, procedures and further information on AE reporting.

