12.3 Reporting Procedures for Serious Adverse Events

All SAEs occurring during the trial must be reported to GW with any other supporting information and recorded in the AE section of the eCRF. Any ongoing SAEs should be followed up until resolution wherever possible. For all deaths, the working diagnosis or cause of death as stated on a death certificate, available autopsy reports and relevant medical reports should be sent to GW promptly.

All SAEs must be recorded in the eCRF within 24 hours of discovery or notification of the event. GW PVD will be automatically notified that an SAE has been recorded. Any additional information required for a case (follow-up or corrections to the original case) will be requested by GW PVD through eCRF queries.

The investigator should continue to document all AEs which occur up to the last formal follow-up observational period (Visit 8). If the investigator subsequently becomes aware of any deaths or a new IMP-related SAE after the last formal follow-up period of the trial, these should still be reported to the GW PVD.

EudraCT Number: 2019-003369-16 Clinical Protocol Global V3, 23Mar2021

Any other problem discovered after Visit 8 that is deemed to be an unexpected safety issue and is likely to have an impact on participants who have taken part in the trial must be treated as an SAE and reported to the GW PVD. Such post-trial SAEs do not need to be recorded on the participant's eCRF if editing rights to the eCRF have been removed due to final trial data lock. GW PVD may request safety follow-up information after the final trial visit in order to investigate a potential safety issue.

Contact details for the GW PVD are provided at the front of the site files for all trial sites.

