12.6 Reporting Procedures for All Adverse Events

All AEs (including SAEs) occurring during the trial will be reported on the running logs in the AE section of the eCRF. This includes all events from the time following screening (Visit 1) up to and including the post-trial follow-up visit (Visit 8), whether attributed to IMP or not and observed by the investigator or participant.

The following information will need to be provided for all AEs:

A) Adverse Event (Diagnosis or Syndrome if Known, or Signs and Symptoms)

Where the investigator cannot determine a diagnosis, signs or symptoms should be recorded in the AE section of the eCRF. Once a diagnosis has been determined the AE section of eCRF must be updated to reflect the diagnosis in replacement of the original symptoms. In circumstances where only a provisional diagnosis is possible (working diagnosis), the eCRF must be updated to reflect the provisional diagnosis in replacement of the original symptoms. In some circumstances it may be relevant for the investigator to include the symptoms alongside the diagnosis in the verbatim event description. However, the diagnosis (full or provisional) should be clearly stated, e.g., fever and malaise due to respiratory tract infection.

B) Adverse Event Start Date and Stop Date

The start and stop dates of the event must be provided. All AEs require these fields to be completed in full. Partial dates or missing dates are not normally acceptable and significant effort must be undertaken to obtain any unknown information. If a precise date is not known an estimated date should be provided instead. When a complete date cannot be given, record as much information as possible (i.e., month and year or,

Confidential Page 72 of 104 Clinical Protocol Template (Phase 2–4)

EudraCT Number: 2019-003369-16 Clinical Protocol Global V3, 23Mar2021

in exceptional circumstances, just year). When the actual start date becomes known the eCRF must be updated to replace the previously recorded date.

C) Outcome

The outcome of the event must be recorded accurately and classified as either:

- Fatal.
- Not recovered/Not resolved.
- Recovered/Resolved.
- Recovered/Resolved with sequelae.
- Recovering/Resolving.
- Unknown.

D) Severity

When describing the severity of an AE the terms mild, moderate, or severe should be used (see below). Clinical judgment should be used when determining which severity applies to any AE.

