5.1.1.1 Handling of Missing Data for the Efficacy Endpoints

Efficacy endpoints will be based on all participants included in the analysis set using all available longitudinal data, either complete or partial. If a participant prematurely discontinues IMP during the treatment period but continues in the study, the data collected after their discontinuation of IMP will be used in the analysis of the efficacy endpoints.

For CGI-S and CGI-I, the score 0 (= not assessed) will be set to missing.

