5.7.2 Adverse Events

All reported AEs will be classified by system organ class (SOC), preferred term and lower level term using Version 24.1 of MedDRA.

Summaries will be presented by treatment group as well as SOC and preferred term.

A treatment period treatment emergent AE (TEAE) is defined as an AE with a start date on or after the first dose of IMP during the treatment period (Day 1), or an AE that was present prior to the first dose of IMP during the treatment period but has increased its intensity during the treatment period.

If an AE has a partial start date and it is unclear from the partial date (or the stop date) whether the AE started prior to or post first dose of IMP then the AE will be considered treatment emergent and if it is unclear which period the event started, it will be assigned to both periods.

An AE will be considered treatment-related if the plausibility relationship to IMP is recorded on the CRF as 'yes'. If the data on plausibility relationship to IMP is missing then the AE will be considered treatment-related.

An AE will be considered leading to permanent discontinuation of IMP if the action taken with IMP is recorded on the CRF as 'trial medication stopped' or the outcome is recorded on the CRF as 'patient died'.

An AE will be considered leading to IMP dose reduction excluding permanent discontinuation if the action taken with IMP is recorded on the CRF as 'dose reduced', 'dose reduced temporarily' or 'trial medication interrupted'.

An AE will be considered leading to temporary IMP dose reduction if the action taken with IMP is recorded on the CRF as 'dose reduced temporarily'.

An AE will be considered leading to permanent IMP dose reduction excluding permanent discontinuation if the action taken with IMP is recorded on the CRF as 'dose reduced'.

An AE will be considered fatal if the outcome is recorded on the CRF as 'patient died'.

For the summary of TEAEs by maximal severity, for each participant, the worst severity recorded by preferred term, SOC and overall will be used for summary purposes. If severity is missing, the worst case (severe) will be assumed.

For summaries by resolution, AEs with an outcome of 'recovered' or 'recovered with sequelae' will be summarized as 'Resolved' and AEs with an outcome of 'continuing', 'patient died' or those with a missing outcome will be summarized as 'Not resolved'.

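### AE recording is tied to Visit 8, which for a participant who stops IMP early but stays in the trial can precede one to three remaining visits; the sections conflict, and late off-drug events are not separated from other TEAEs

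*Protocol*

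**What the plan says.** **Text that ends recording at Visit 8.** Protocol 12.1.1 limits an AE to events occurring after screening and "at any point up to the post-treatment, safety follow-up visit (Visit 8". Protocol 12.3 says: "The investigator should continue to document all AEs which occur up to the last formal follow-up observational period (Visit 8". After that point 12.3 still requires deaths, new IMP-related SAEs, and unexpected safety issues likely to affect participants. Protocol 12.6 describes the AE log as including events "up to and including the post-trial follow-up visit (Visit 8".

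**When that contact happens.** Under Protocol 4.1, a participant who stops IMP early attends an end-of-treatment visit and must "complete the safety follow-up visit 2 weeks after their last dose. Participants are encouraged to attend any outstanding visits per the trial schema". Note a to Appendix 1 and SAP 3.1 say the same.

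**Text that implies recording continues.** Protocol 9.1.16 covers "All AEs occurring during the trial, whether attributed to the IMP or not". Protocol 12.3 opens by requiring every SAE in the trial to be reported. The Appendix 1 AE row marks every visit from 2 to 8.

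**How the SAP classifies the events.** In SAP 5.7.2 a new-onset TEAE is "an AE with a start date on or after the first dose of IMP during the treatment period (Day 1", with no end date. The worsening limb is confined to the treatment period, which SAP 5.1.3.4 fixes at Day 1 to Day 85 whatever the last dose date. The TEAE rule in Protocol 13.6.4.2 has no upper limit. SAP 5.7.2 bases time-of-onset percentages on safety-set participants with a visit or call in each interval. For efficacy, SAP 5.1.1.1 states that "the data collected after their discontinuation of IMP will be used in the analysis of the efficacy endpoints".

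**The concern.** The Visit 8 wording fits a participant treated to Day 85, for whom Visit 8 is the last contact. It does not fit someone who stops IMP early and keeps attending, and the trial wants to keep that person because the later efficacy data are analysed. Whether AEs over the same weeks are captured then depends on which section the site follows.

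Each reading has a cost:

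- **Recording ends at the early Visit 8.** Non-serious AEs, and non-fatal SAEs judged unrelated, need not be recorded at the later visits. The participant still counts in the onset-interval denominators, so late-interval percentages are diluted.
- **Recording continues.** A new event many weeks after the last dose enters the TEAE tables beside on-drug events, and nothing in SAP 5.7.2 or the table list separates the two.

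**Working it through.** **Inputs.** Visits 4, 5, 6 and 7 are on Days 15, 29, 57 and 85 and Visit 8 is on Day 99 (Appendix 1; SAP Table 2). Safety follow-up is last dose + 14 days (Protocol 4.1). Randomised: 80 (SAP 3.2).

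**1. The plan's own figure.** For a participant treated to Day 85, Visit 8 = 85 + 14 = Day 99, as stated.

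**2. Early stoppers.** With last dose on Day L, Visit 8 falls on Day L + 14. Follow-up left to Day 85 is 85 − (L + 14) days. Time off drug at Day 85 is 85 − L days.

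| Last dose (L) | Visit 8 | Visits after it | Days from Visit 8 to Day 85 | Days off drug at Day 85 |
|---|---|---|---|---|
| Day 1 | Day 15 | 5, 6, 7 | 70 | 84 |
| Day 15 | Day 29 | 6, 7 | 56 | 70 |
| Day 29 | Day 43 | 6, 7 | 42 | 56 |
| Day 43 | Day 57 | 7 | 28 | 42 |
| Day 57 | Day 71 | 7 | 14 | 28 |
| Day 70 | Day 84 | 7 | 1 | 15 |
| Day 71 | Day 85 | none | 0 | 14 |

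Three visits remain if L + 14 < 29 (L < 15), two if L is 15 to 42, one if L is 43 to 70, and none from Day 71. The ±3-day window on Visit 8 moves that last boundary to about Day 68 to 74. For L = 15, 56/84 = 67% of the 84-day treatment span lies after Visit 8.

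**3. What each section requires at a visit after an early Visit 8.**

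| Event | 12.1.1 and closing part of 12.3 | 9.1.16, opening of 12.3, Appendix 1 |
|---|---|---|
| Death, new IMP-related SAE, unexpected safety issue | report | report |
| Non-fatal SAE judged unrelated | outside the window | report |
| Non-serious AE | outside the window | record |

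The conflict is confined to the last two rows.

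**4. Denominators.** Take L = 15 and a participant who attends Visits 6 and 7. Day 57 falls in the Weeks 9–12 interval (Days 57 to 84) and Day 85 in the interval beyond Day 84. The participant counts in both denominators, although on the literal definition AE recording closed on Day 29. If k of n participants in an interval are present but unobserved for AEs, and event risk is otherwise equal, the observed percentage is the true one multiplied by (n − k)/n.

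**5. Size, under a stated assumption.** Allocation 2:2:1:1 gives 80 × 2/6 ≈ 27 per active arm. The documents do not say how many stopped IMP and stayed. If 5% to 15% did, that is 4 to 12 of 80, or about 1 to 4 of 27. With everyone else still attending, the multiplier runs from 26/27 = 0.96 to 23/27 = 0.85. This is an upper bound on dilution, since some would stop on or after Day 71. If the events are recorded instead, one such participant moves an arm's TEAE incidence by 1/27 = 3.7 percentage points.

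**The case against.** The strongest reply is that most of the operative text already points to continued recording. Protocol 12.3 opens with all SAEs in the trial, and its reduced rule applies after the trial's last formal follow-up, which hardly describes someone still attending Visit 6. Protocol 12.6 starts from all AEs in the trial and only then says that this includes events to Visit 8, which illustrates more than it caps. The trial schema also has a Day 99 contact. The documents do not say whether a continuing participant receives it as well; if so, and if that contact is what Visit 8 means, the gap closes.

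Much of this stands. A reader might infer that AE collection simply stops, or that SAEs such as an unrelated hospitalisation are lost. The documents do not support that: they contradict themselves, and deaths, IMP-related SAEs and unexpected issues stay reportable on any reading. What the reply does not remove is the definition in 12.1.1, which names Visit 8 as the end and has no exception for participants who continue.

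A reader might also infer that the TEAE rule has no end at all, or that it must be capped at last dose + 14 days. Neither follows. The worsening limb ends at Day 85. Counting all post-baseline events is a legitimate convention and matches Protocol 13.6.4.2, so a cap in the SAP alone would create a new disagreement with the protocol. AE listings also give start and stop days, so timing can be traced by hand.

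**Conclusion.** The point holds as a conflict between sections with a bounded consequence. For a last dose before about Day 71, the literal AE definition excludes non-serious AEs and unrelated non-fatal SAEs found at one to three visits that the protocol encourages and the efficacy analysis uses, while other sections require them. The stretch at issue runs from 70 days (last dose Day 1) down to nothing (Day 71); the 56-day example sits towards the long end. Under either reading the SAP falls short: it keeps possibly unobserved participants in the onset denominators, or it mixes new events up to 84 days off drug by Day 85 with on-drug events.

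The count of 4 to 12 participants rests on an assumed 5% to 15%. The plan's 15% drop-out figure describes a different group and does not support it. A reader might infer a bias for or against the drug. That would need IMP stopping to differ between arms, and nothing in the documents shows whether it did; the TEAE tables are in any case descriptive. The change is worth making because it is cheap and safety reporting should not turn on which section a site read.

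**What to change.** - **Protocol 12.1.1, 12.3 and 12.6:** reconcile with 9.1.16 and Appendix 1 so that AE and SAE recording runs to the later of the safety follow-up contact and the last trial visit attended. State whether a continuing participant also has the Day 99 contact.
- **SAP 5.7.2, classification:** keep the TEAE definition consistent with the protocol. Add a flag and one summary splitting TEAEs into onset through last dose + 14 days (the protocol's own follow-up length) and later onset, labelled post-treatment.
- **SAP 5.7.2, denominators:** drop a participant from any onset interval in which AEs were not collected.
- **SAP or study report:** state how AEs after an early Visit 8 were collected among the 80 randomised, and how many participants this concerned.

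The cost is a few sentences, one flag and one extra summary. Because the study ended early, protocol rewording cannot recover events that were not collected; the SAP changes and the statement on collection are what still help.

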12.1.2 Investigator

The term investigator refers to the trial PI or a formally delegated trial physician.

12.2 Serious Adverse Events

During clinical investigations, AEs may occur which, if suspected to be IMP-related, might be significant enough to lead to important changes in the way the IMP is developed (e.g., change in dose, population, monitoring need, consent forms). This is particularly true for events that threaten life or function. Such SAEs will be reported promptly to regulatory authorities, applicable IRBs/IECs and investigators (expedited reporting) by GW.

An AE must only be classed as serious, i.e., an SAE, when the event falls into 1 of the following criteria:

- Results in death.
- Is life-threatening. (The term "life-threatening" in the definition of "serious" refers to an event in which the participant was at risk of death at the time of the event; it does not refer to an event which, hypothetically, might have caused death if it were more severe.)

Confidential Page 69 of 104

Study Code: GWAP19030 EudraCT Number: 2019-003369-16 Clinical Protocol Global V3, 23Mar2021

- Requires inpatient hospitalization or prolongation of existing hospitalization. (AEs requiring hospitalization should be considered serious. In general, hospitalization signifies that the participant has been detained [usually involving an overnight stay] at a hospital or emergency ward for observation and/or treatment which would not have been appropriate at the trial site. When in doubt as to whether hospitalization occurred or was necessary, the AE should be considered as serious.)
- Results in persistent or significant disability/incapacity (disability is defined as a substantial disruption of a person's ability to conduct normal life functions).
- Is a congenital anomaly/birth defect.
- Is medically significant. (Medical and scientific judgment should be exercised in deciding whether SAE reporting is appropriate in other situations. Important medical events may not be immediately life-threatening or result in death or hospitalization but may jeopardize the participant or may require intervention to prevent one of the other outcomes listed in the definition above. These should also usually be considered serious. Examples of such events are intensive treatment in an emergency room or at home for allergic bronchospasm, blood dyscrasias or convulsions that do not result in hospitalization, development of drug dependency or use of drugs of abuse, or positive COVID-19 test.)

